12.1.7 Technical complaints

A technical complaint is any written, electronic, or oral communication that alleges product (medicine or device) defects. The technical complaint may be associated with an AE, but does not concern the AE itself.

Examples of technical complaints:

- The physical or chemical appearance of trial products (e.g. discoloration, particles or contamination)
- All packaging material including labelling
- Problems related to devices (e.g. to the injection mechanism, dose setting mechanism, push button or interface between pen and needle)

12.2 Reporting of adverse events

All events meeting the definition of an AE must be collected and reported. This includes events from the first trial-related activity after the patient has signed the informed consent until the end of the post-treatment follow-up period (visit 17). The events must be recorded in the applicable eCRF forms in a timely manner, see timelines below and [Figure 12-1](#)

During each contact with the trial site staff, the patient must be asked about AEs and technical complaints, for example by asking: “Have you experienced any problems since the last contact?”

All AEs, either observed by the investigator or patient, must be reported by the investigator and evaluated. All AEs must be recorded by the investigator on an AE form. The investigator should report the diagnosis, if available. If no diagnosis is available, the investigator should record each sign and symptom as individual AEs using separate AE forms.

For SAEs, a safety information form must be completed in addition to the AE form. If several symptoms or diagnoses occur as part of the same clinical picture, one safety information form can be used to describe all the SAEs.

AESIs regardless of the seriousness, must be reported using the AE form and safety information form

Protocol
 Trial ID: NN7415-4255
 UTN: U1111-1179-3872
 EudraCT no.: 2016-000614-29

~~CONFIDENTIAL~~

Date: 28 December 2017 | **Novo Nordisk**
 Version: 4.0
 Status: Final
 Page: 87 of 124

For all non-serious AEs, the applicable forms should be signed when the event is resolved or at the end of the trial at the latest.

Timelines for initial reporting of AEs:

The investigator must complete the following forms in the case report form (CRF)/eCRF within the specified timelines:

- **SAEs:** The AE form **within 24 hours** and the safety information form **within 5 calendar days** of the investigator's first knowledge of the SAE.

[figure not shown]
Both forms must be signed within 7 calendar days from the date the information was entered in the eCRF.

For SAEs requiring reporting on a specific event form: In addition to the above the specific event form within **14 calendar days** from the investigator's first knowledge of the AE.

- **Non-serious AEs fulfilling the AESI criteria:** The AE form and safety information form **within 14 calendar days** of the investigator's first knowledge of the event.

If the eCRF is unavailable, the concerned AE information must be reported on a paper AE form and sent to Novo Nordisk by fax, e-mail or courier within the same timelines as stated above. When the eCRF becomes available again, the investigator must enter the information on the form into the eCRF.

Contact details (fax, telephone, e-mail and address) are provided in the investigator trial master file.

Timelines are for the completion of forms from the time of investigator's awareness
 AEs requiring specific event forms are described in Section 12.1.5 and 12.1.6

AE: Adverse event **AESI:** Adverse event of special interest **SIF:** Safety information form

Protocol
 Trial ID:NN7415-4255
 UTN:U1111-1179-3872
 EudraCT no.:2016-000614-29

~~CONFIDENTIAL~~

Date:	28 December 2017	Novo Nordisk
Version:	4.0	
Status:	Final	
Page:	88 of 124	

Figure 12–1 Reporting of AEs

Novo Nordisk assessment of AE expectedness:

Novo Nordisk assessment of expectedness is performed according to the following reference documents: Investigator’s Brochure; Current version and any updates thereto.

Reporting of trial product-related SUSARs by Novo Nordisk:

Novo Nordisk will notify the investigator of trial product-related suspected unexpected serious adverse reactions (SUSARs) in accordance with local requirements and ICH GCP¹. In addition, the investigator will be informed of any trial-related SAEs that may warrant a change in any trial procedure.

In accordance with regulatory requirements, Novo Nordisk will inform the regulatory authorities, including EMA, of trial product-related SUSARs. In addition, Novo Nordisk will inform the International Review Boards/Independent Ethics Committees (IRBs/IECs) of trial product-related SUSARs in accordance with local requirement and ICH GCP¹, unless locally this is an obligation of the investigator.

Novo Nordisk products used as concomitant medication or non-investigational medicinal product:

If an AE is considered to have a causal relationship with a Novo Nordisk marketed product used as non-investigational medicinal product rFVIII (turoctocog alfa) *or* concomitant medication in the trial, it is important that the suspected relationship is reported to Novo Nordisk, e.g. in the alternative aetiology section on the safety information form. Novo Nordisk may need to report this adverse event to relevant regulatory authorities.

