12.7 Rules for putting enrolment on hold

If one of below mentioned criteria is fulfilled, enrolment of additional patients in the clinical trial program will be placed on hold. An urgent safety committee meeting will be scheduled to decide further actions. Dosing of patients on treatment may continue while further evaluation is made by the safety committee. A substantial amendment with relevant data must be submitted to the regulatory authorities to support restart of the trial.

- Significant thromboembolic event*
- Event of DIC
- Anaphylactic reaction related to trial drug administration
- Death of trial patient which may be related to the trial product
- Two or more other trial product related SAEs similar in nature have been reported and/or detected by laboratory measurements
- Trends in AEs, clinical observations or laboratory parameters which raise concerns about the safety of continued treatment

Protocol
 Trial ID:NN7415-4255
 UTN:U1111-1179-3872
 EudraCT no.:2016-000614-29

~~CONFIDENTIAL~~

Date:	18 December 2017	Novo Nordisk
Version:	3	
Status:	Final	
Page:	93 of 124	

* Superficial thrombophlebitis or venous thrombosis associated with indwelling catheters is not considered a significant thromboembolic event unless evaluated as such by the investigator

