5.3 Treatment of patients

Table 5–1 List of products provided by Novo Nordisk

Compound Name	Strength	Dosage form	Route of administration	Treatment period
Concizumab B²,	100 mg/mL	3 mL solution in a 3 mL cartridge ³ .	S.c. administration using NovoPen [®] 4	For prophylactic treatment for 76 weeks.
Turoctocog alfa (NovoEight[®])⁴, Sodium chloride solution 4ml	2000 IU/vial	Powder for solution for injection Solvent for solution for i.v. injection used for reconstitution of turoctocog alfa.	I.v. administration	For treatment of breakthrough bleeding episodes (or prophylaxis in the screening and follow-up phases), at the discretion of the treating physician (patients may choose to use other familiar pre-trial FVIII drug). For further information see section 5.3.2

Concizumab will be given s.c., once daily for a total dosing period of 76 weeks.

The NovoPen[®]4 injector will be supplied by Novo Nordisk and used for the s.c. administration of concizumab. It will be labelled in accordance with national legislation and a copy of the label can be found within the Trial Materials Manual, see Section [9.1](#).

The first dose of concizumab will be given at the trial site under medical supervision. After the initial dose the patient must be observed for potential emergence of AEs/safety signals for at least 2 hours at the trial site. At the screening visit and the first scheduled treatment visit patients will be trained in s.c. administration of concizumab with NovoPen[®] 4 and in the use of eDiary.

Investigational medicinal product (IMP)

³ Not to be confused with the daily injected volume (~150 µL, depending on dose strength and body weight)

⁴ Non-investigational medicinal product (NIMP)

Protocol
 Trial ID: NN7415-4255
 UTN: U1111-1179-3872
 EudraCT no.: 2016-000614-29

~~CONFIDENTIAL~~

Date:	28 December 2017	Novo Nordisk
Version:	4.0	
Status:	Final	
Page:	34 of 124	

In case safety concerns meet the criteria (See section [12](#)) for putting enrolment of additional patients on hold, further enrolment in the trial will be halted. Dosing of patients on treatment may continue while further evaluation is made by the safety committee. In case of other safety concerns all available data will be evaluated by the DMC see Section [12.8.2](#).

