12.1.2 Serious adverse event

A serious adverse event (SAE) is an experience that at any dose results in any of the following:

- Death.
- A life-threatening^a experience.
- In-patient hospitalisation^b or prolongation of existing hospitalisation.
- A persistent or significant disability or incapacity^c.
- A congenital anomaly or birth defect.
- Important medical events that may not result in death, be life threatening^a or require hospitalisation^b may be considered an SAE when - based on appropriate medical judgement - they may jeopardise the patient and may require medical or surgical intervention to prevent one of the outcomes listed in the definition of SAE^d.

^a. The term “life threatening” in the definition of SAE refers to an event in which the patient was at risk of death at the time of the event. It does not refer to an event which hypothetically might have caused death if it was more severe.

^b. The term “hospitalisation” is used when a patient:

- Is admitted to a hospital or in-patient, irrespective of the duration of physical stay, or
- Stays at the hospital for treatment or observation for more than 24 hours

Protocol
 Trial ID: NN7415-4255
 UTN: U1111-1179-3872
 EudraCT no.: 2016-000614-29

~~CONFIDENTIAL~~

Date:	28 December 2017	Novo Nordisk
Version:	4.0	
Status:	Final	
Page:	80 of 124	

Medical judgement must always be exercised, and when in doubt, the hospital contact should be regarded as a hospitalisation. Hospitalisations for administrative, trial related and social purposes do not constitute AEs and should therefore not be reported as AEs or SAEs. Hospital admissions for surgical procedures, planned before trial inclusion, are not considered AEs or SAEs.

^c A substantial disruption of a patient's ability to conduct normal life functions (e.g. following the event or clinical investigation the patient has significant, persistent or permanent change, impairment, damage or disruption in his body function or structure, physical activity and/or quality of life).

^d For example intensive treatment in an emergency room or at home of allergic bronchospasm, blood dyscrasia or convulsions that do not result in hospitalisation or development of drug dependency or drug abuse.

The following adverse events must always be reported as an SAE using the important medical event criterion if no other seriousness criteria are applicable:

- Suspicion of transmission of infectious agents via the trial product

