12.1.6 Adverse event of special interest

An adverse event of special interest (AESI) is an event, which in the evaluation of safety, has a special focus. In this trial, the following AEs fulfil the AESI criteria:

- Thromboembolic events including but not limited to,
 - disseminated intravascular coagulation (DIC) (A),
 - clinical signs or laboratory indications of arterial and venous thrombosis including myocardial infarction (B),
 - pulmonary embolism (C),
 - stroke (D),
 - deep vein thrombosis (E),
 - other clinically significant thromboembolic events (F) and peripheral artery occlusion (see below G), see definitions below.

The AESIs must be reported on an AE form and a safety information form.

Protocol
 Trial ID:NN7415-4255
 UTN:U1111-1179-3872
 EudraCT no.:2016-000614-29

~~CONFIDENTIAL~~

Date:	28 December 2017	Novo Nordisk
Version:	4.0	
Status:	Final	
Page:	83 of 124	

A) Definition of disseminated intravascular coagulation (DIC), as defined below:

The definition of DIC in this trial should be made according to the International Society on Thrombosis and Haemostasis (ISTH) criteria. Thus, a DIC diagnosis may be based on clinical signs and symptoms of a bleeding tendency or thrombotic tendency, organ dysfunction and the laboratory parameters criteria as listed below:

- Platelet count ($>100 \times 10^9/L = 0$, $<100 \times 10^9/L = 1$, $<50 \times 10^9/L = 2$)
- Elevated D-dimer (no increase = 0, moderate increase = 2, strong increase = 3)
- Prolonged PT ($<3 \text{ s} = 0$, $>3 \text{ but } <6 \text{ s} = 1$, $>6 \text{ s} = 2$)
- Fibrinogen level ($>1 \text{ g/L} = 0$, $<1 \text{ g/L} = 1$)
- Calculate score: ≥ 5 compatible with overt DIC

(B) Myocardial infarction is defined according to the “Third Universal Definition of Myocardial Infarction”²⁴

Criteria for acute myocardial infarction - The term acute myocardial infarction (MI) should be used when there is evidence of myocardial necrosis in a clinical setting consistent with acute myocardial ischemia. Under these conditions any one of the following criteria meets the diagnosis for MI:

- Detection of a rise and/or fall of cardiac biomarker values [preferably cardiac troponin (cTn)] with at least one value above the 99th percentile upper reference limit (URL) and with at least one of the following:
 - Symptoms of ischemia.
 - New or presumed new significant ST-segment–T wave (ST–T) changes or new left bundle branch block (LBBB).
 - Development of pathological Q waves in the ECG.

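### A significant thromboembolic event or DIC puts enrolment on hold, but if classed as non-serious it need not be reported to the sponsor for 14 days

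*Protocol*

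**What the plan says.** **Hold rule.** Section 12.7 says that if any one listed criterion is met, "enrolment of additional patients in the clinical trial program will be placed on hold", and an urgent safety committee meeting is scheduled. The first criterion is a "Significant thromboembolic event", with a footnote: "Superficial thrombophlebitis or venous thrombosis associated with indwelling catheters is not considered a significant thromboembolic event unless evaluated as such by the investigator". The second is an event of DIC, without any qualifier. Neither criterion asks whether the event is serious. These words are cited from version 3 (18 December 2017). The copy of version 4.0 (28 December 2017) at hand ends in section 12.5, but its contents list 12.7, and its section 5.3 repeats that when the section 12 criteria are met, "further enrolment in the trial will be halted".

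**AESI category.** Section 12.1.6 makes thromboembolic events the AESIs of this trial. The category includes DIC and "clinical signs or laboratory indications of arterial and venous thrombosis including myocardial infarction".

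**Reporting limits.** Section 12.2 requires the same two forms for every AESI but sets the time limit by seriousness. For an SAE the AE form is due within 24 hours and the safety information form within 5 calendar days. For "Non-serious AEs fulfilling the AESI criteria" both forms are due within 14 calendar days. Versions 3 and 4.0 agree. Section 12.3 sets 14 calendar days for AESI follow-up, including an already reported non-serious AE that later meets the AESI criteria.

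**Always-serious list.** Section 12.1.2 has a list introduced by "The following adverse events must always be reported as an SAE using the important medical event criterion". It contains suspected transmission of an infectious agent and liver injury by Hy's law, and nothing else.

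**The concern.** A hold rule can act only on events that the sponsor knows of. Section 12.7 treats a single event as urgent enough to stop enrolment and convene the safety committee. Section 12.2 gives the same event, if judged non-serious, the longest initial reporting limit in that section. Section 12.4.1 asks for a technical complaint unrelated to any SAE within 5 calendar days, so a pen fault has a shorter limit than a non-serious event that triggers the hold.

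The events are the ones this program has most reason to watch. Section 18.1 names thromboembolism as the potential risk from the toxicity studies. Section 3.1.2 reports falls in fibrinogen and marked rises in D-dimer in the preceding multiple-dose trial, and both are components of the DIC score in section 12.1.6. At stake are the timing of the urgent committee review, the timing of the program-wide hold, and the number of new patients who start in the meantime.

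**Working it through.** There is no planned sample size or error rate to reproduce here. The check is a comparison of sections, followed by a short calculation for scale.

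**1. Limits side by side**

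| Report | First form due | Second form due | Section |
|---|---|---|---|
| SAE | AE form, 24 hours | Safety information form, 5 calendar days | 12.2 |
| Non-serious AESI | AE form, 14 calendar days | Safety information form, 14 calendar days | 12.2 |
| Technical complaint related to an SAE | 24 hours | none | 12.4.1 |
| Any other technical complaint | 5 calendar days | none | 12.4.1 |

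**2. Can a hold trigger be a non-serious AESI?** The hold criteria carry no seriousness condition, and both triggers fall within the AESI category. The protocol itself provides for non-serious AESIs. Two cases are conceivable. One is a deep vein thrombosis shown on ultrasound (12.1.6, item E) and managed without admission. The other is a DIC diagnosis resting largely on the laboratory score: a strong D-dimer increase (3) plus a prothrombin time prolonged by more than 6 seconds (2) gives 3 + 2 = 5, the score compatible with overt DIC. Whether either is an SAE then depends on the important-medical-event criterion in 12.1.2, which is a matter of judgement.

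**3. Does any other rule set a shorter binding limit?**
- The always-serious list in 12.1.2 does not name these events.
- Section 6.4 requires discontinuation of trial product for a thromboembolic event or DIC. Section 8.1.4 then asks for an IWRS session, without a time limit.
- Section 13.2 (version 3) prefers eCRF entry within 5 days of the visit but does not require it.
- Section 8.5 sends coagulation samples to central laboratories but sets no alert to the sponsor. Platelet counts are analysed locally.
- Section 12.7 contains no immediate-notification rule of its own.

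None of these binds the site to a shorter limit.

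**4. Scale**

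Inputs: 33 patients planned to start (6.1); planned first patient first visit 16 August 2017 and last patient first visit 16 December 2017 (section 7), which is 122 days. Assume uniform accrual and a site that uses the whole limit.

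Expected starts during a reporting lag = 33 x lag / 122:
- 14 days: 33 x 14/122 = 3.8
- 5 days: 33 x 5/122 = 1.4
- 1 day: 33 x 1/122 = 0.3

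The 14-day limit is 14/122 = 11% of the planned recruitment window.

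**5. Timing against the protocol version**

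The 122 days run between screening visits. Visit 2, the first dose, follows 14 to 21 days later (8.1.9.1). The last planned first dose therefore falls between 30 December 2017 and 6 January 2018, which is 2 to 9 days after the date of version 4.0. At 33/122 = 0.27 patients per day, that leaves 0.27 x 2 = 0.5 to 0.27 x 9 = 2.4 planned starts under version 4.0. The 3.8 is thus a rate at the planned pace, not a count for the period that version 4.0 governs.

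**The case against.** The strongest reply is that the hold triggers and the AESIs are different sets. AESIs are wider: they include laboratory indications of thrombosis and suspected events. The hold asks for a significant event and leaves out superficial and catheter-associated thrombosis unless the investigator judges otherwise. A slower route for non-serious AESIs can serve events that would never trigger a hold. A confirmed deep vein thrombosis or overt DIC would plausibly be judged an important medical event and go on the 24-hour limit. The DIC definition also draws on clinical signs and organ dysfunction, not the score alone. This stands, and it confines the point to events that are both hold-triggering and classed as non-serious. It does not remove the point, because that classification is left to judgement.

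A second reply is that other safeguards work regardless of the form deadline. The affected patient must be discontinued, patients are trained to report signs of thrombosis at once, and an independent data monitoring committee reviews data. Even during a hold, "Dosing of patients on treatment may continue while further evaluation is made by the safety committee", so faster reporting would not by itself stop dosing of others. All of this is correct. None of it tells the sponsor sooner by rule, and the decision on further actions belongs to the urgent committee meeting that the report sets in motion.

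A third reply is that the reporting flow in Figure 12-1 and section 12.7 of version 4.0 cannot be read in the copy at hand. This limits certainty about version 4.0. Version 3 contains both rules in readable text.

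**Conclusion.** The point holds in a narrow form. No rule that can be read puts every hold-triggering event on the SAE reporting limit, so a significant thromboembolic event or DIC judged non-serious may formally reach the sponsor up to 14 days after the site knows of it. The consequence is a possible two-week delay to the urgent committee review and to a hold that covers the clinical trial program.

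Three stronger readings are not supported. A reader might infer that every thromboembolic AESI triggers the hold and takes the slow route; the significance condition, the exclusions and the SAE route rule that out. A reader might infer that about four more patients would start in this trial; 3.8 assumes uniform accrual over screening dates and full use of the limit, and on plan only about 0.5 to 2.4 starts remained after version 4.0. A reader might infer that 12.2 and 12.7 contradict each other; they can both be followed as written, and 14 days is an outer limit. What is missing is a link between them.

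**What to change.** Reconcile section 12.2 with section 12.7. In 12.2, apply the existing SAE reporting limit (AE form within 24 hours, safety information form within 5 calendar days of the investigator's first knowledge) to any AESI that meets a hold criterion in 12.7, regardless of seriousness. Applying it to all AESIs is simpler for sites, because they then need not decide whether a hold criterion is met before choosing the limit. In 12.3, align the follow-up limit, including for a previously reported non-serious AE that later meets the AESI criteria. Bring Figure 12-1 into line if it shows the 14-day route.

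The cost is a wording change, a short instruction to sites and a few more expedited forms. The all-AESI option brings in some events that would not trigger a hold, such as laboratory indications of thrombosis, so it adds more forms than the narrower one. The change concerns reporting only and leaves clinical management as it is.

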12.3 Follow-up of adverse events

The investigator must record follow-up information by updating the forms in the eCRF.

Follow-up information must be reported to Novo Nordisk according to the following:

- **SAEs:** All SAEs must be followed until the outcome of the event is “recovered/resolved”, “recovered/resolved with sequelae” or “fatal”, and until all queries have been resolved. Cases of chronic conditions, cancer or AEs ongoing at time of death (where death is due to another AE) may be closed with the outcome “recovering/resolving” or “not recovered/not resolved”. Cases can be closed with the outcome of “recovering/resolving” when the patient has completed the follow-up period and is expected by the investigator to recover.

The SAE follow-up information should only include new (e.g. corrections or additional) information and must be reported **within 24 hours** of the investigator’s first knowledge of the

Protocol
 Trial ID: NN7415-4255
 UTN: U1111-1179-3872
 EudraCT no.: 2016-000614-29

~~CONFIDENTIAL~~

Date:	28 December 2017	Novo Nordisk
Version:	4.0	
Status:	Final	
Page:	89 of 124	

information. This is also the case for previously non-serious AEs which subsequently become SAEs.

- **Non-serious AEs:** Non-serious AEs must be followed until the outcome of the event is “recovering/resolving”, “recovered/resolved” or “recovered/resolved with sequelae” or until the end of the follow-up period stated in the protocol, whichever comes first, and until all queries related to these AEs have been resolved. Cases of chronic conditions, cancer or AEs ongoing at time of death (where death is due to another AE) may be closed with the outcome “recovering/resolving” or “not recovered/not resolved”. Cases can be closed with the outcome of “recovering/resolving” when the patient has completed the follow-up period and is expected by the investigator to recover.
- **Non-serious AEs fulfilling the AESI criteria:** Non-serious AE fulfilling the AESI criteria must be followed as specified for non-serious AE. Follow-up information on AESIs should only include new (e.g. corrections or additional) information and must be reported **within 14 calendar days** of the investigator’s first knowledge of the information. This is also the case for previously reported non-serious AEs which subsequently fulfil the AESI criteria.

The investigator must ensure that the recording of the worst case severity and seriousness of an event is kept throughout the trial. A worsening of an unresolved AE must be reported as follow up with re-assessment of severity and/or seriousness of the event.

Queries or follow-up requests from Novo Nordisk must be responded to **within 14 calendar days** from the date of receipt of the request, unless otherwise specified in the follow-up request.

SAEs after end of trial: If the investigator becomes aware of an SAE with a suspected causal relationship to the investigational medicinal product occurring to a patient after the patient has ended the trial, the investigator should report this SAE within the same timelines as for SAEs during the trial.

